- **Duration of IGA of 0** = the date of first observation of IGA > 0 - the date of first observation of IGA of 0 and stop treatment. The duration of IGA of 0 for subjects who end treatment in IGA success will be censored at the last disease assessment date. This is for subjects who achieve IGA of 0 and stop the treatment. Subjects who achieve IGA of 0 but never stop treatment will be excluded from the analysis. For subjects who achieve IGA of 0 but stop the treatment later, the duration starts from the date of stop treatment. Only the first IGA of 0 duration will be analyzed.
- **Duration of IGA of 0 or 1** = the date of first observation of IGA > 1-the date of first observation of IGA of 0 or 1 + 1. The duration of IGA of 0 or 1 for subjects who end treatment in IGA of 0 or 1 will be censored at the last disease assessment date. Only the first IGA of 0 or 1 duration will be analyzed.
- **Disease recurrence** = the date of first observation of IGA of 2 or above after achieving IGA of 0 and stop treatment - the date of first observation of IGA of 0 + 1. Only the first disease recurrence will be analyzed.
- **Treatment-free interval** = the date of re-starting study drug due to IGA score above 0 - the date of stop treatment due to attainment of score of IGA of 0 +1, among subjects who achieve a “completely clear” IGA and stop treatment to all lesions. If subjects never re-start study drug after stopping treatment, the treatment-free interval is censored at the end of study date. Only the first treatment-free interval will be analyzed.
- **Weight of IP (g)** = dispensed can weight – returned can weight.
- **BMI (kg/m²)** = (weight in kg)/[(height in cm/100)²]. Day 1 height will be used for BMI derivation upto Week 24. For visits including week 24 through week 36, week 24 height

will be used to derive BMI. Week 52 BMI is derived using the height and weight collected at the same visit. This derivation is applied since height is not collected at all visits.

- **BMI Categories:**

- Underweight: $BMI < 18.5$
- Normal: $18.5 \leq BMI \leq 24.9$
- Overweight: $25.0 \leq BMI \leq 29.9$
- Obese: $BMI \geq 30.0$

- **WI-NRS 4-point reduction** = achievement of a 4-point reduction in WI-NRS pruritus score post-baseline compared to baseline, calculated only for subjects with a pruritus score of ≥ 4 at baseline.
- **Itch-free state** = achievement of in WI-NRS of 0 or 1.

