Duration of IGA success, for subjects whose IGA grade is not 0 or 1 at OLE baseline, is defined as the time from the first observation of IGA success to first subsequent time a subject's disease response does not meet the criteria for IGA Success. The duration of IGA success for subjects who end treatment in IGA success will be censored at the last disease assessment date. Only the first IGA success duration will be analyzed.

If there is no IGA assessment after the first observation of IGA success, the duration will be censored at the end of study date.

The median time (number of days) for IGA success will be analyzed using the Kaplan–Meier method. Subjects who discontinue study without relapse will be considered censored in the Kaplan–Meier analyses. The Kaplan–Meier estimate will be stratified by the IGA success time (IGA success by Week 4, between Week 4 and Week 12, between Week 12 and Week 24, between Week 24 and Week 36, and between Week 36 and Week 52).

Duration of IGA success will be summarized by Cohort, Groups, and overall.

The analysis of duration of IGA of 0 or 1 will be performed in the similar fashion.

Duration of IGA of 0 will be performed for subjects who achieve IGA of 0 post OLE baseline and stop treatment. Subjects who achieve IGA of 0 but never stop treatment will be excluded from analysis. If subject achieved IGA of 0 but stop treatment several days later, the duration

will start at the IP stop date. The analysis of duration of IGA of 0 will be in the similar fashion as the analysis for duration of IGA success.

Similar analysis from primary baseline will be performed.

Disease recurrence

This analysis will be performed using IGA assessments during the open-label study.

Time to disease recurrence is defined as time from first observation of IGA of 0 and stop treatment to first observation of IGA of 2 or higher after stop treatment. Subjects who achieve IGA of 0 but never stop treatment will be excluded from analysis. If subject achieve IGA of 0 but stop treatment several days later, the duration will start at the IP stop date. If there is other IGA assessment after achieving IGA of 0, the time to disease recurrence will be censored at the last disease assessment date. If there is no IGA assessment after the first observation of IGA success, the duration will be censored at the end of study date. The analysis of time to disease recurrence will be in the similar fashion as the analysis of duration of IGA success.

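### Duration of IGA of 0 and disease recurrence rest on a drug stop that need not be for clearance, and recurrence has two different time origins

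*SAP*

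**What the plan says.** Three variables in SAP 6.1.7 (Derived Variables) describe what happens after a subject clears and stops drug.

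- **Treatment-free interval** runs from "the date of stop treatment due to attainment of score of IGA of 0". The reason for the stop is part of the definition.
- **Duration of IGA of 0** deals with a delayed stop as follows: "For subjects who achieve IGA of 0 but stop the treatment later, the duration starts from the date of stop treatment". The only exclusion is "Subjects who achieve IGA of 0 but never stop treatment will be excluded from the analysis". There is one censoring rule: "The duration of IGA of 0 for subjects who end treatment in IGA success will be censored at the last disease assessment date".
- **Disease recurrence** ends at the first IGA of 2 or above "after achieving IGA of 0 and stop treatment - the date of first observation of IGA of 0 + 1". The stop is mentioned, but the subtraction uses the first IGA of 0.

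SAP 8.2.1 describes the last two again. For Duration of IGA of 0 it begins "If subject achieved IGA of 0 but stop treatment several days later, the duration" and then sets the start at the IP stop date. For recurrence it says "If subject achieve IGA of 0 but stop treatment several days later, the duration will start at the IP stop date".

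**The concern.** These analyses should show how long skin stays clear once drug is withdrawn because it is clear. For two of the three variables the text asks only that the subject reached IGA 0 and stopped drug, then or later. It gives no reason for the stop, no limit on the delay, and no requirement that IGA is still 0 when drug stops. For Duration of IGA of 0 it also does not say that the end event must come after the stop.

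A subject who lost clearance while still applying drug, and later stopped for something else, can therefore enter as a loss of clearance off drug. Protocol 5.4.3 lists several such reasons, including adverse events, subject decision and prohibited medication. Under Protocol 6.4 a subject withdrawn from the study has a termination visit with the Week 52 procedures, which include IGA, so an assessment soon after an unrelated stop is likely.

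Separately, 6.1.7 and 8.2.1 start the recurrence clock at different dates. Two programmers following the SAP could produce different curves.

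**Working it through.** The documents state no figure for these variables, so there is none to reproduce. The check applies the SAP's own definitions to hypothetical subjects. Days 29, 85 and 169 are scheduled visits (Weeks 4, 12 and 24); Days 120 and 122 are chosen for illustration.

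**Subject A.** IGA 0 on Day 29, keeps applying, IGA 2 on Day 85, drug stopped for an adverse event on Day 120, IGA 2 at termination on Day 122.

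| Variable and source | Formula | Result |
|---|---|---|
| Duration of IGA of 0, literal | first IGA above 0, minus stop: 85 - 120 | -35 days |
| Duration of IGA of 0, post-stop IGAs only | 122 - 120 | 2 days |
| Recurrence, 8.2.1 | first IGA of 2 or above after the stop, minus stop: 122 - 120 | 2 days |
| Recurrence, 6.1.7 | same event, minus first IGA 0, plus 1: 122 - 29 + 1 | 94 days |
| Treatment-free interval, 6.1.7 | stop not due to IGA 0 | not eligible |

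Section 8.2.1 states no added day; adding 1, as 6.1.7 does for recurrence, makes its result 3 days. The 94 days consist of 120 - 29 = 91 days between clearing and stopping, 2 days after the stop, and the added day. The IGA 2 on Day 122 is not IGA success, so the censoring rule does not remove this subject.

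**Subject B.** IGA 0 on Day 29, stops on Day 32 for clearance, IGA 2 on Day 85. Duration of IGA of 0 is 85 - 32 = 53 days. Recurrence is 85 - 32 = 53 days under 8.2.1 and 85 - 29 + 1 = 57 under 6.1.7. The two origins disagree even for a genuine clearance stop.

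**Subject C.** IGA 0 on Day 29 without stopping, IGA 1 on Day 85, IGA 0 and a clearance stop on Day 169. If the first IGA above 0 is taken literally, Duration of IGA of 0 is 85 - 169 = -84 days. Adding a reason for the stop would not cure this; the end event must also be restricted to assessments after the stop. Recurrence is not exposed here, because both sections place its end event after the stop.

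**After the change below.** Subject A leaves both analyses. Subject B keeps a Duration of IGA of 0 of 53 days and has a single recurrence origin, Day 32. Subject C starts on Day 169, with only later assessments counted.

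**Sensitivity, on assumed inputs only.** Suppose a share f of the analysis set has an event at time 0, and true off-drug times are exponential with median m and no censoring. The Kaplan-Meier median becomes m × (1 + log2(1 - f)). With m = 120 days, f = 5%, 10% and 20% give 111, 102 and 81 days. The documents give neither f nor m.

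**The case against.** The strongest reply is that a clearance stop is meant throughout. SAP 2.2.1.2 and 8.2.1 define even the treatment-free interval with the same shorthand, reaching IGA 0 and stopping treatment, and only 6.1.7 spells out the reason. The wording in 8.2.1 points to a lag of days, not months. Protocol 5.6.3 and 6.5 have subjects stop once the investigator confirms clear. A spurious event therefore needs a subject who clears, keeps applying, loses clearance on drug and stops later for another reason. This is fair as to intent and numbers. It does not supply the missing condition, and the SAP itself provides for subjects who clear and stop late or never.

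A reader might infer that every stop for an adverse event, failure or end of treatment becomes an instant relapse. The documents do not support that:

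- Subjects still at IGA 0 are not events. Those who end treatment in IGA success are censored for Duration of IGA of 0. A subject who entered at IGA 3 or above and ends at IGA 1 would normally be censored, and IGA 1 is never a recurrence.
- The near-zero recurrence time arises only under 8.2.1. Section 6.1.7 gives a long time instead.
- Scheduled end of treatment is probably not meant as a stop. If it were, the exclusion of subjects who never stop would remove almost nobody. The SAP should still say so.

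It may also be argued that the error is conservative. That holds for spurious early events, but the 6.1.7 recurrence formula errs the other way by adding time on drug.

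**Conclusion.** The point holds in a limited form. Followed literally, the SAP gives a negative or near-zero Duration of IGA of 0 for a subject who lost clearance on drug and later stopped for another reason. It also gives two recurrence times for the same subject, 2 and 94 days in the worked case. The recurrence conflict needs no assumption about why drug was stopped.

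The practical effect is probably small. Neither variable is in the endpoint lists of Protocol 4.2.2 or SAP 2.2, SAP 6.1.2 plans no inference, and the protocol's instruction to stop when clear limits the number affected. The documents do not give the share of such subjects, so a shift in the Kaplan-Meier curve can be computed only from assumed shares; the sensitivity figures are not estimates for this trial. The change is still worth making: SAP 10 shows that the duration variables were deliberately redefined, so they are intended outputs.

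**What to change.** Amend SAP 6.1.7 and 8.2.1 together, for Duration of IGA of 0 and disease recurrence:

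1. Define the qualifying stop as the subject's first IP stop made for investigator-confirmed clearance, with the most recent IGA equal to 0.
2. State that scheduled end of treatment, and stops for any other reason, do not qualify.
3. Start the clock at that stop in both sections, replacing the first-IGA-0 origin for recurrence in 6.1.7.
4. Count only IGA assessments after that stop towards the end event.

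The cost is SAP wording, and a few non-qualifying subjects leave the two analyses. No new data appear to be needed: 6.1.7 already uses investigator confirmation of clear as a recorded reason for missed doses. This assumes that the record identifies the stop date. Treatment conduct is unaffected.

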5.6.3. Treatment Administration

Seborrheic dermatitis lesions that have completely resolved, in the opinion of the Investigator, do not require continued treatment. At every clinic visit the Investigator will determine if the IGA are considered ‘clear’ and the subject will stop applying the investigational product. The subject will contact the clinical study site and document in diary when seborrheic dermatitis returns prior to restarting investigational product. Subjects that clear between scheduled visits should return for an unscheduled visit for the Investigator to confirm IGA score are considered ‘clear’.

Unless otherwise instructed by the Investigator, subjects will apply investigational product once daily. At the Day 1 visit, the study staff will demonstrate to the subject how to apply ARQ-154 foam using the first Can from the Kit that is provided to the subject at Day 1. Study site staff will be trained to ensure a proper amount is dispensed from the foam Can and applied to seborrheic dermatitis lesion(s) as a thin layer and rubbed in thoroughly but gently, until the foam has disappeared. **For scalp lesions, special attention should be given to ensuring adequate investigational product is applied to scalp skin and not rubbed off on hair.** The subject will then practice dispensing a similar amount of investigational product and applying to seborrheic dermatitis lesion(s). The study staff will confirm that the subject’s application technique is correct. Cohort 1 Group 2 subjects will apply the last dose of IP for ARQ-154-116 Week 2 (Day 15) study visit; subjects will enroll in ARQ-154-214 on the same day but will start applying IP the following day (Day 2). The study staff will review with the subject the appropriate IP

dispensing and application technique for the ARQ-154-214 study during the Baseline visit (Day 1).

IP will be applied in the evening to areas of lesions of seborrheic dermatitis. IP will be applied at least 20 minutes before going to bed.

For Scalp Lesions: IP will be applied when the skin and hair on the scalp is dry. Subjects should dispense IP on their fingers, then part hair where there are lesions and rub IP into scalp skin. As the IP is applied, the subject should move any hair away to ensure that sufficient foam is actually applied directly to the affected skin on the scalp. Subjects should not use other hair products for at least an hour before or after application.

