6.5. Unscheduled Visit

Subjects that clear between scheduled visits should return for an unscheduled visit for the Investigator to confirm IGA score are considered 'clear' and subject will stop application of investigational product after Investigator confirmation. Subjects will call the site when seborrheic dermatitis returns prior to restarting application of investigational product. Unscheduled visits may also be necessary to repeat testing following abnormal laboratory

results, for follow-up of AEs, or for any other reason, as warranted in the judgment of the Investigator.

The following information will be collected for all subjects:

- AEs
- Concomitant medications/procedures

The following information will be collected for those subjects that had stopped study medication but are experiencing a reoccurrence of seborrheic dermatitis. These subjects may have an unscheduled visit (although an unscheduled visit is not required as subjects only need to call the site) when seborrheic dermatitis returns prior to restarting application of investigational product:

- IGA

An updated Body Diagram of seborrheic dermatitis involvement should be provided to the subject.

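### Time to disease recurrence and duration of IGA 0 do not stop when drug is restarted, so a return of disease re-treated without an IGA can be missed or dated late

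*SAP*

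**What the plan says.** SAP 6.1.7 (Derived Variables) restricts duration of IGA 0 to subjects who clear and stop: "This is for subjects who achieve IGA of 0 and stop the treatment". Its length is "the date of first observation of IGA > 0 - the date of first observation of IGA of 0 and stop treatment", and on censoring the SAP says: "The duration of IGA of 0 for subjects who end treatment in IGA success will be censored at the last disease assessment date".

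For disease recurrence, SAP 6.1.7 sets the end at "the date of first observation of IGA of 2 or above after achieving IGA of 0 and stop treatment". SAP 8.2.1 gives the same end point, "first observation of IGA of 2 or higher after stop treatment", and excludes subjects who never stop. If a later IGA exists but shows no recurrence, "the time to disease recurrence will be censored at the last disease assessment date". If there is no later IGA, censoring is at the end of study. Neither section names restart of study drug as an event or as a censoring time.

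Protocol 5.6.3 describes how drug is restarted: "The subject will contact the clinical study site and document in diary when seborrheic dermatitis returns prior to restarting investigational product". Protocol 6.5 lists the IGA among the data for a visit at recurrence, but makes that visit optional: "although an unscheduled visit is not required as subjects only need to call the site". The same two sections have a subject whom the investigator finds clear stop applying drug, at a scheduled or an unscheduled visit.

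**The concern.** Because both variables admit only subjects who are clear and off drug, a reader will take their curves as showing how long clearance lasts after stopping. Restarting drug acts like rescue: it can remove the event being measured before anyone has graded it. If the return is reported by telephone, no IGA exists at that time. The next IGA is then taken after a period back on drug. If that IGA is below the threshold, the return is not counted and the clock runs on through re-treatment. If it is at or above the threshold, the event is counted late and in a subject who is no longer off drug. Both errors lengthen the curve. SAP section 10 also records that the duration variables were redefined to end at the first loss of response. Letting the clock run past re-treatment works against that intention.

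**Working it through.** **No figure to reproduce.** The documents give no median, event count or precision for these variables. SAP 3.2 says the sample size rests on no such calculation.

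**Gaps between scheduled IGAs** (Protocol 1.3 and 5.3: Weeks 4, 12, 24, 36, 52): 12 − 4 = 8, 24 − 12 = 12, 36 − 24 = 12 and 52 − 36 = 16 weeks. The phone visits at Weeks 18, 30 and 44 cover only adverse events and concomitant medication (Protocol 6.1.11). SAP 6.1.3 rules out imputing an IGA that was not taken.

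**Unscheduled IGAs.** SAP 6.1.4 admits an unscheduled measurement only when the scheduled one is missing. SAP 8.2.1 expressly includes unscheduled visits in its summaries of response at any time, but is silent on them for the duration analyses.

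**Worked subject.** Clear and stopped on Day 85 (Week 12); disease returns and drug restarts by phone on Day 113; IGA 0 on Days 169, 253 and 365. Because the clear date and the stop date coincide, it does not matter that SAP 6.1.7 and 8.2.1 start the recurrence clock differently.

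- Time to recurrence under the SAP (end − start + 1): 365 − 85 + 1 = 281 days, censored.
- Same formula, ended at restart: 113 − 85 + 1 = 29 days.
- Time credited after restart: 281 − 29 = 252 days.
- Re-treatment within that time: the subject is clear on Day 169 and stops again under Protocol 5.6.3, so 169 − 113 = 56 days (8 weeks).
- Duration of IGA 0, whose formula has no + 1: 365 − 85 = 280 days, censored, against 113 − 85 = 28 days to restart.

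**Simulation of time to recurrence.** The inputs are assumptions, not taken from the documents. Off-drug recurrence is exponential with a median of 56 days. Drug is stopped at Day 29, 85 or 169 (40%, 40%, 20%) and restarted on the day of recurrence. After restart there is a 10% or 30% chance of IGA 2 or above at each scheduled visit. There is no dropout and no stopping again at later clear visits. Each scenario has 4,000 subjects.

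| Restarts with a qualifying IGA recorded | Kaplan-Meier median under the SAP rule (days) | Recurrence-free at Day 168 |
|---|---|---|
| 100% | 58–59 | 12% |
| 75% | 81–85 | 29–31% |
| 50% | 130–169 | 43–51% |
| 25% | 197 to not reached | 57–70% |
| 0% | 281 to not reached | 73–90% |

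The true value at Day 168 is about 12%, since 168 days is three half-lives and 0.5³ = 0.125. Counting restart as an event gives medians of 55 to 59 days and 11% to 13% recurrence-free at Day 168. With 50% recorded, true medians of 28 and 112 days become 85–93 and 220–293 days.

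**Plain censoring at restart.** If only a share p of recurrences is recorded and the rest are censored on the same day, the estimated hazard is p times the true hazard, so the median is 56/p. At p = 0.5 this is 112 days, and the simulation gave 110–112. Such censoring is informative.

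**Allowing for stopping again.** A separate run for duration of IGA 0 used a stop at Week 12, a true median of 56 days, and 50%, 75% or 90% regaining control. With no IGA at restart, the share of returns never counted fell from 40%, 59% and 71% to 17%, 37% and 53% once subjects stopped again at each clear visit. With an IGA at 30% of restarts, it fell from 28%, 40% and 50% to 11%, 20% and 28%, and the medians were still 102 to 168 days.

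**The case against.** The strongest reply is that the unscheduled visit exists for this purpose and its listed content includes the IGA. The SAP also words the treatment-free interval as if an IGA value is known at restart. If every restart had a qualifying IGA and the analysis used it, there would be almost no bias. That is correct, and it is why the size is conditional. But the visit is optional, and the SAP does not say that unscheduled IGAs enter these analyses.

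A second reply is that the treatment-free interval already measures time off drug and ends at restart. It does, and it is the listed endpoint. It remains a separate output that does not correct the other two curves. Its restart trigger also differs within the SAP (IGA above 0 in 6.1.7; 2 or above in 2.2.1.2 and 8.2.1), and neither version fits a phone restart with no IGA.

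A third reply is that a restart need not mean recurrence. This stands. SAP 6.1.7 contemplates restart at any IGA above 0, so counting every restart as an IGA of 2 or above would mislabel a subject measured at IGA 1. It would also make the variable nearly a copy of the treatment-free interval.

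A reader might also infer that everything credited after restart is time on drug. The protocol does not support that, because a subject found clear stops again. In the worked case 56 of the 252 days need be on drug.

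**Conclusion.** The point holds as a defect in two derivations. Followed as written, they can count re-treated time as off-drug remission and date some recurrences late. The direction is towards longer apparent durability. The size cannot be fixed from the documents, because the share of restarts with an IGA is not given. On the stated assumptions it runs from almost nothing (58–59 days against a true 56) to a median that is not reached. Stopping again at clear visits reduced the share missed in the run shown, but the medians stayed too long.

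A reader might conclude that these analyses can say nothing about how long clearance lasts, or that the trial's conclusions are at risk. Neither follows. With complete recording at restart the curves are sound. Both variables are descriptive, in a single-arm study with no inferential analysis, and neither is among the listed endpoints in Protocol 4.2 or SAP 2.2. The primary endpoints, TEAEs and SAEs, and the sample size are untouched.

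**What to change.** In SAP 6.1.7 and 8.2.1, state that no time after the first restart of study drug is counted, and then:

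- **Duration of IGA 0:** event at the earlier of the first IGA above 0 or restart for returned disease.
- **Time to disease recurrence:** event at the earlier of the first IGA of 2 or above while off drug, or restart for returned disease with no IGA taken. Where an IGA of 1 was recorded at restart, end follow-up there and report it separately as a competing event, not as recurrence.
- **Supportive analysis:** plain censoring at restart may be shown, labelled as informative censoring, but should not be the main result.
- **Unscheduled IGAs:** state that they are used in these analyses.
- **Reporting:** give the number of restarts with and without an IGA.

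The cost is SAP wording and one more date in two derivations. The restart date is already needed for the treatment-free interval and for expected applications, so no new data and no change to subject management are required. The downside is that reported durations will be shorter and some events will rest on a subject's own report that disease has returned.

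### SAP 6.1.7 starts time to disease recurrence at first IGA 0, but SAP 8.2.1 starts later stoppers at the drug stop date; the 6.1.7 start adds event-free time on drug

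*SAP*

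**What the plan says.** **SAP 6.1.7, Disease recurrence.** The formula runs "first observation of IGA of 2 or above after achieving IGA of 0 and stop treatment - the date of first observation of IGA" of 0; in full, the date subtracted is "the date of first observation of IGA of 0 + 1. Only the first disease recurrence will be analyzed". The event therefore requires treatment stop; the start date does not.

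**SAP 8.2.1, Disease recurrence.** The definition is "time from first observation of IGA of 0 and stop treatment to first observation of IGA of 2 or higher after stop treatment". For a subject who stops after clearing: "If subject achieve IGA of 0 but stop treatment several days later, the duration will start at the IP stop date". On the analysis set: "Subjects who achieve IGA of 0 but never stop treatment will be excluded from analysis".

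**Neighbouring bullets in SAP 6.1.7.** Duration of IGA of 0 carries the later-stop rule: "For subjects who achieve IGA of 0 but stop the treatment later, the duration starts from the date of stop treatment". Treatment-free interval starts at the date treatment is stopped. The Disease recurrence bullet has neither provision.

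**Protocol 5.6.3.** At each clinic visit the Investigator decides whether the IGA is clear, "and the subject will stop applying the investigational product". Under Protocol 6.5, subjects who clear between visits come in for confirmation and stop after it.

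**SAP section 10.** The listed change to the duration variables concerns where an interval ends (first loss of response instead of last instance), not where it starts. It does not settle the difference.

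**The concern.** Under the 6.1.7 formula a subject must reach the stop date before an IGA of 2 or above can count. The days between first IGA 0 and a later stop enter the time variable but can hold no event, which is immortal time. An IGA of 2 or above seen in that window, while the subject is still applying drug, would be ignored although its days are counted.

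The SAP does not say which section prevails, and a list of derived variables is a natural source for programming. Two programmers working from different sections could produce different Kaplan-Meier curves for the same subjects, and the 6.1.7 version would attribute on-drug time to durability off drug.

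**Working it through.** The plan states no figure to reproduce: the sample size is not based on power or precision, and this is a matter of definition. The check is date arithmetic.

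**Inputs.** A = study day of first IGA 0; S = IP stop day; R = day of first IGA of 2 or above after the stop. Visit days come from the Schedule of Visits: Week 4 = 29, Week 12 = 85, Week 24 = 169, Week 36 = 253.

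**Formulas.**
- SAP 6.1.7: R − A + 1.
- SAP 8.2.1: R − max(A, S) + 1. Section 8.2.1 does not state the + 1; it is carried over here so that only the start date differs.
- Difference: max(A, S) − A, which is 0 if S = A and S − A if S is later.

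| Case | A | S | R | 6.1.7 | 8.2.1 | Difference |
|---|---|---|---|---|---|---|
| Stop on day of first IGA 0 | 85 | 85 | 169 | 85 | 85 | 0 |
| Stop one week later | 85 | 92 | 169 | 85 | 78 | 7 |
| IGA 0 at Week 4, stop at Week 12 | 29 | 85 | 169 | 141 | 85 | 56 |
| IGA 0 at Week 12, stop at Week 24 | 85 | 169 | 253 | 169 | 85 | 84 |

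A censored subject's time is lengthened by the same lag, because only the start moves.

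**Effect on the Kaplan-Meier median.** This was simulated under assumptions that are not in the documents: exponential time from stop to recurrence with a true median of 60 or 120 days, first IGA 0 at Day 29 or Day 85 with equal probability, censoring at Day 365, and a fixed lag in a stated share of subjects. Entries are the median under 6.1.7 minus the median under 8.2.1, in days, taken before rounding.

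| Lag | Share who stop late | True median 60 | True median 120 |
|---|---|---|---|
| 7 days | 10% | 0.7 | 0.7 |
| 7 days | 25% | 1.8 | 1.8 |
| 7 days | 50% | 3.6 | 3.6 |
| 56 days | 10% | 7.6 | 6.5 |
| 56 days | 25% | 17.9 | 15.7 |
| 56 days | 50% | 32.4 | 30.1 |

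The median moved toward longer times in every scenario.

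**The case against.** The strongest reply is that 8.2.1 is the full specification (analysis set, event, censoring, method) and already starts later stoppers at the stop date. With the later-stop rule also present in the adjacent Duration of IGA of 0 bullet, the recurrence bullet looks like an incomplete short form. That is a fair reading of intent. It does not remove the literal conflict, and the SAP gives no order of precedence.

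The second reply is that the lag should seldom matter. Under Protocol 5.6.3 and 6.5 a subject stops once the Investigator confirms clearance, so first observed IGA 0 and the stop should usually fall on the same visit. This stands. The SAP nevertheless provides for later stoppers, by several days in its own description, so the case is foreseen.

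Three stronger readings are tempting, and the documents do not support them:
- *That off-drug time to recurrence is a main message of the study.* The objective is safety, and disease recurrence appears in none of the endpoint lists (Protocol 4.2; SAP 2.2).
- *That the listed off-drug endpoint is affected too.* Treatment-free interval already starts at the stop date in 6.1.7, so this start-date error does not reach it.
- *That inflation of 56 or 84 days is to be expected.* Such a lag means a subject recorded as clear kept applying drug until the next scheduled clinic visit, contrary to the protocol's instruction. The documents give no frequency for this.

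**Conclusion.** The inconsistency is real, and 6.1.7 is wrong as written: it pairs an event that can occur only off drug with a clock that may start on drug. For each subject the excess is exactly the lag from first IGA 0 to stop. It is zero for same-day stoppers, who should be the majority if the protocol is followed, and positive for anyone later. The bias is therefore always toward a longer time to recurrence.

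With lags of about a week, the simulated median moves by 0.7 to 3.6 days when 10% to 50% of subjects stop late. With 56-day lags in the same shares it moves by 6.5 to 32.4 days. Both ranges rest on assumed lags, shares and recurrence rates, and the second also presumes departures from the protocol.

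The consequence is limited to one descriptive estimate that is not a listed endpoint. No hypothesis test, primary safety result or sample-size statement depends on it. This is a minor point, worth correcting because the correction is so cheap.

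**What to change.** In the Disease recurrence bullet of SAP 6.1.7, replace the start date with *the later of the date of first IGA of 0 and the IP stop date*. This agrees with 8.2.1 for later stoppers and leaves same-day stoppers unchanged. Taking the later of the two also covers a subject whose last application was the evening before the clearing visit.

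State the + 1 in 8.2.1 as well, or drop it from both sections. Changing only the start date in 6.1.7 would leave a one-day mismatch between them.

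The cost is one line in 6.1.7 and a few words in 8.2.1. No new data are needed, provided the IP stop date is recorded as 8.2.1 already presumes, and study conduct does not change.
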